307 blood glucose twice daily (fasting before breakfast and at bedtime) and report the
308 readings to the study coordinator on a bi-weekly base.
309

310 **Rationale for study Design**

311 The randomized, double-blind, placebo-controlled study design will allow for an
312 independent and unbiased effect of liraglutide on study results.
313

314

315 **Rationale for minimum study time line of 3 weeks.**

316 The pre-operative clinic schedule may not always allow to wait the full 12 weeks between
317 the patient's enrollment and the CABG, standard of care procedure. [name] is the only
318 cardiac surgeon at UM performing elective CABGs. Once the patient is randomized and
319 randomly allocated to one of the study arms, the length of the treatment is set by the date
320 of standard of care CABGs. During the current COVID-19 pandemic, the number of
321 elective CABGs has been reduced and we cannot reschedule or delay the surgery
322

323 **Study Population:** Study group will be formed by 40 patients with T2DM and with
324 clinically and angiographically stable CAD who will undergo CABG surgery, as part of
325 their standard medical care. Cardiac surgery will be elective procedure in
326 hemodynamically stable patients taking their standard cardiac treatments and under the
327 care of the cardiologist.

328

329 **Study team and site:** [name] is Professor of Medicine, Division of
330 Endocrinology, Diabetes and Metabolism. [name] pioneered EAT echocardiographic
331 measurement and he is considered the leading expert in the epicardial fat. [name] will
332 lead and supervise liraglutide therapy, EAT measurement, analysis and interpretation of
333 the data. [name], Research Assistant Professor, Dept. Microbiology and Immunology,
334 will lead and supervise adipose tissue analysis. [name] is associate professor
335 of Cardiology and contributes to patient recruitment. [name], professor of
336 cardiothoracic surgery will be the cardiac surgeons for this study. Low calorie diet (LCD)
337 and other nutritional aspects will be managed and supervised by the Division of
338 Endocrinology registered dietitian (RD), as part of the standard care. University of Miami
339 has been the site of several National Health Institute (NIH) studies and many peer-reviewed
340 publications. The Division of Endocrinology Diabetes and Metabolism is fully equipped
341 and trained to visit, follow up and manage patients with diabetes. The Division of

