541 identifying information. All data used in the analysis and reporting of this evaluation will
542 be without identifiable reference to the patient. Data used for reports or publications will
543 never include identifiable information such as name, date of birth, social security number,
544 address, or medical record number and in most cases will not include any identifiers other
545 than sex, age, race, and diagnosis.

546 **Scheduling CABG timing**

547 In patients with stable CAD found to have CAD anatomy that requires CABG, the timing
548 and schedule for revascularization will be determined by [name]. Patients suitable to
549 wait between 3 and 12 week- period for revascularization will be identified and managed
550 with optimal medical therapy, and scheduled for complete revascularization with CABG.

551 **Managing patients becoming unstable or developing acute events during the study**

552 The inclusion and exclusion criteria will limit the possibility of recruiting patients with
553 unstable CAD/angina, as defined before. Study patients showing unstable angina or
554 developing acute cardiac events will be transferred promptly to the local emergency
555 department for evaluation and treatment. If patient status becomes acute and emergent, the
556 adverse event will be reported to the IRB.

557 **Unblinding**

558 The investigator will follow the study's randomization procedures. The blind should
559 ordinarily be broken for serious and unexpected adverse experiences that are associated
560 with the use of a drug to determine if there is a reasonable possibility that the experience
561 may have been caused by the drug. Certain adverse events such as ***known consequences***
562 ***of the underlying disease under investigation*** or events common in the study population
563 generally should ***not*** require unblinding.

564 We feel that in the not likely case (given the inclusion criteria) that a study patient will
565 become unstable or develop acute events during the study, this event would more likely
566 fall in the ***known consequences of the underlying disease under investigation*** rather than
567 caused by the study drug, and therefore should ***not*** require premature unblinding.
568 Nevertheless, it will be upon the principal investigator's best judgement and discretion to

569 break the blind. In this case, the principal investigator will promptly document and report
570 to the IRB and Novo Nordisk any premature unblinding.

571

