734 investigator's discretion.

735 **Adverse Events**

736 In the case of an adverse event (AE), the investigator will comply with all local legal,
737 regulatory, and IRB requirements. The investigator will report to IRB all adverse events
738 including not serious and serious adverse events (SAE), suspected unexpected serious
739 adverse reactions (SUSARs), serious adverse drug reactions (SADRs). The investigator
740 will report all SAEs, SUSARs, and SADRs at the same time such events are reported to
741 regulatory authorities or within 15 days from the investigator becoming aware of such
742 adverse events, whichever comes first.

743 The investigator will use the approved Updated Prescribing Information for Victoza®. The
744 investigator will collect the following information at minimum for each of these events: 1.
745 Study name2. Patient identification 3. Event (preferably a diagnosis) 4. Drug 5. Reporter
746 identification. 6. Causality 7. Outcome

747 **Definitions** An AE is any undesirable medical event occurring to a subject in a clinical
748 trial, whether or not related to the trial product(s). This includes events reported from the
749 first trial related activity after the subject has signed the informed consent and until post
750 treatment follow-up period as defined in the protocol. The following should not be recorded
751 as AEs, if recorded as medical history/concomitant illness at screening:
752 • Pre-planned procedure, unless the condition for which the procedure was planned has worsened from
753 the first trial related activity after the subject has signed the informed consent
754 • Pre-existing conditions found as a result of screening procedures

755 Clinical Laboratory Adverse Event: A clinical laboratory AE is any clinical laboratory
756 abnormality regarded as clinically significant i.e. an abnormality that suggests a disease
757 and/or organ toxicity and is of a severity, which requires active management, (i.e. change
758 of dose, discontinuation of trial product, more frequent follow-up or diagnostic
759 investigation).

760 **Serious Adverse Event (SAE):** A serious AE is an experience that at any dose results in
761 any of the following:

- 762 • Death
- 763 • A life-threatening* experience
- 764 • In-patient hospitalization or prolongation of existing hospitalization

765 Suspicion of transmission of infectious agents must always be considered an SAE
766 • A persistent or significant disability/incapacity

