767 • A congenital anomaly/birth defect
768 • Important medical events that may not result in death, be life-threatening*, or require
769 hospitalisation may be considered an SAE when, based upon appropriate medical
770 judgement, they may jeopardise the subject and may require medical or surgical
771 intervention to prevent one of the outcomes listed in this definition

772 *The term life-threatening in the definition of SAE refers to an event in which the subject
773 was at risk of death at the time of the event. It does not refer to an event which
774 hypothetically might have caused death if it was more severe.

775 **SADR:** an adverse drug reaction (ADR) is an adverse event for which a causal relationship
776 (Possible/Probable relation) between the study drug and the occurrence of the event is
777 suspected. The ADR should be classified as serious if it meets one or more of the
778 seriousness criteria.

779 **Medical Events of Special Interest (MESI):** A MESI is (1) a medication error (e.g. wrong
780 drug administration or wrong route of administration) or (2) a suspected transmission of an
781 infectious agent via the product

782 **Non-Serious Adverse Event:** A non-serious AE is any AE which does not fulfil the
783 definition of an SAE. Severity Assessment Definitions:

- 784 • Mild: Transient symptoms, no interference with the subject's daily activities
- 785 • Moderate: Marked symptoms, moderate interference with the subject's daily activities
- 786 • Severe: Considerable interference with the subject's daily activities, unacceptable

787 Relationship to study medication Assessment Definitions:

- 788 • Probable: Good reasons and sufficient documentation to assume a causal relationship
- 789 • Possible: A causal relationship is conceivable and cannot be dismissed
- 790 • Unlikely: The event is most likely related to an etiology other than the trial product

791 **Outcome Categories and Definitions:** • Recovered: Fully recovered or by medical or
792 surgical treatment the condition has returned to the level observed at the first trial related
793 activity after the subject signed the informed consent• Recovering: The condition is
794 improving and the subject is expected to recover from the event. This term should only be
795 used when the subject has completed the trial • Recovered with sequelae: As a result of the
796 AE, the subject suffered persistent and significant disability/incapacity (e.g. became

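### The Unblinding section presumes that acute events come from the disease and makes breaking the blind the way to judge drug causation, with no blinded causality rating required first

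*Combined protocol and SAP*

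**What the plan says.** The protocol's Unblinding section contains three statements.

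- General rule: the blind should "ordinarily be broken for serious and unexpected adverse experiences that are associated" "with the use of a drug to determine if there is a reasonable possibility that the experience" was drug-caused. Recognised consequences of the disease, and events common in this population, generally do not call for unblinding.
- Presumption: should a patient "become unstable or develop acute events during the study, this event would more likely" belong with the effects of the disease than be "caused by the study drug, and therefore should *not* require premature unblinding".
- Discretion: "Nevertheless, it will be upon the principal investigator's best judgement and discretion to" break the blind. Any premature unblinding is documented and reported to the IRB and the drug supplier.

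The Adverse Events section makes causality one of the minimum items collected for each event ("identification. 6. Causality 7. Outcome"). The scale is Probable, Possible or Unlikely. The SADR definition rests on that rating: the relevant words are "Possible/Probable relation) between the study drug and the occurrence of the event is", followed by the requirement that such a link be suspected.

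Under Study team and site, one person is to "lead and supervise liraglutide therapy, EAT measurement, analysis and interpretation of" the data. The section on reliability of the echocardiographic measurement names two readers, a physician and a cardiac imaging technician, and blinds both to clinical data. It does not mention the treatment arm.

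**The concern.** A causality rating is most useful when the rater does not know the arm. Two features of the Unblinding section work against that, in different ways.

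The first is the order of steps. If the code is broken in order to judge causation, the rating is made with the arm known. Similar events may then be rated differently in the two arms.

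The second is the presumption. It is written before any event has occurred, and it closely resembles the definition of Unlikely, which applies when another cause is the most probable one. A rater who carries it over to the causality item would tend to place acute events outside the SADR category. The patients have coronary disease and wait 3 to 12 weeks for bypass surgery, so acute cardiac events are a foreseeable safety question.

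A smaller matter is the echocardiographic endpoint. If the person who learns the arm also measures epicardial fat, a follow-up scan could be read with the arm known.

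**Working it through.** The plan gives no cardiac event rate, unblinding rate or safety sample size, so there is no figure to reproduce. The check is mainly a reading of the sections against each other.

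**1. Which events are rated with the arm known?** The general rule covers serious, unexpected, drug-associated events, and for these the stated purpose of the code break is to judge causation. For acute cardiac events the default is to stay blinded. They are rated with the arm known only if the principal investigator uses the discretion allowed. The two features therefore mostly concern different events.

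**2. What does the presumption do to the rating?** Unlikely means that another cause is the most probable one. Possible needs only that a drug link is conceivable and cannot be ruled out. An acute event in a blinded patient could fit either, and the presumption points to Unlikely. If applied while blinded, it would push both arms the same way, lowering the count of SADRs without favouring an arm. Rating after a code break can act differently by arm.

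**3. Does any safeguard come first?** The documents describe no independent adjudication, no data monitoring committee and no rule that causality be recorded before a code break. Statistical Considerations covers gene and protein expression, fat thickness and regressions. It plans no table of events by arm.

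**4. Could a comparison of arms correct wrong ratings?** Input: 20 patients per arm (Power Analysis).

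- Zero events in 20: exact two-sided 95% upper limit = 1 − 0.025^(1/20) = 0.168.
- Fisher two-sided p for k against 0 events = 2 × C(20,k)/C(40,k). For k = 4: 2 × 4,845/91,390 = 0.106. For k = 5: 2 × 15,504/658,008 = 0.047. At least 5 against 0 is needed for p < 0.05.
- Exact Fisher power, assuming a 5% placebo rate and a liraglutide rate of 10%, 15%, 20% or 30%: about 2%, 7%, 17% and 45%.
- Chance of at least one event among 40 patients = 1 − (1 − p)^40. At assumed rates p of 1%, 2%, 5% and 10%: 33%, 55%, 87% and 99%.

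Unless events are very rare, the question is likely to arise, and counts by arm could seldom settle it. These figures describe the sample size. They do not measure misattribution.

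**5. Who may learn the arm?** The principal investigator may break the blind. The title material, the team section and the reader description suggest that this is also the person who leads fat measurement and analysis and may read the scans. Names are removed, so this is an inference. Each patient unblinded before the follow-up scan is 1/20 = 5% of an arm.

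**The case against.** The strongest case on the other side is that the text is milder than it looks and that the safety reporting is sound. Most of that stands.

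A reader might infer that the protocol has already decided that cardiac events are not drug-related. It has not. The sentence is worded as an opinion about what is more likely, it governs unblinding, it assigns no causality code, and discretion follows at once. Because Possible has a low threshold, the presumption is compatible with rating an acute event Possible.

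A reader might also infer that such events would go unreported. The documents say the opposite. Any adverse event goes to the sponsor and IRB (Protection Against Risks), all serious events are reported (Adverse Events), and serious or severe events are followed whatever their causality (Follow-up of Adverse Events).

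Nor is it an error in itself to rate a known placebo patient's event Unlikely, since that patient received no liraglutide. The loss is that the ratings in the two arms are no longer made on the same footing.

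The echocardiographic point is limited too. Both readers are blinded to clinical data, thickness is a secondary endpoint, and the tissue analysis for the primary endpoint is led by a different faculty member. The documents do not show that any scan would be read with the arm known.

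None of this supplies a blinded rating before a code break made to judge causation.

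**Conclusion.** The point holds as a modest one about attribution. Followed as written, the Unblinding section leads to causality ratings made with the arm known for serious, unexpected, drug-associated events. For acute events it adds a presumption close to the definition of Unlikely. What is exposed is the choice between Possible or Probable and Unlikely, which defines an SADR.

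The size of the bias cannot be estimated from the documents. The 16.8% limit and the 5-against-0 result show only that 20 patients per arm leave little chance of correcting individual ratings through group counts. The event rates behind the power figures and the chance of at least one event are assumptions. The link to the fat measurements depends on the principal investigator being the person who leads them, which the redacted text suggests but does not establish.

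**What to change.** 1. Require the causality rating to be recorded and dated before any code break made for reporting. Keep both the blinded rating and any later revision.
2. State in the Unblinding section that the presumption about acute events does not set the causality rating, or delete it.
3. Where a patient's arm becomes known to the investigator before the follow-up scan, use the reading of the second reader already planned, kept blind to arm. Reproducibility is to be assessed in all subjects, so that reading should exist. Report the number of patients unblinded, by arm.

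A descriptive listing of acute cardiac events by arm would be useful but is secondary. Giving the arm only to whoever files the safety report would not solve the problem, because the Adverse Events section makes the investigator that person.

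Code breaks needed for patient care are unaffected. The cost is a few lines of protocol text and a small documentation task.

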380 methods (as required by local law or practice)

381

382 **Investinational drug**

383 Liraglutide [rDNA origin] injection, solution for subcutaneous use. Liraglutide will be
384 prescribed according to the same, current indications of the marketed Victoza.

385

386 **Withdrawal Criteria**

387 1. The subject may withdraw at will at any time.
388 2. The subject may be withdrawn from the trial at the discretion of the investigator due to
389 a safety concern or if judged non-compliant with trial procedures or included in
390 contravention to the inclusion and/or exclusion criteria.
391 3. Subject diagnosed with acute pancreatitis by clinical and/or radiographic criteria.
392 4. Pregnancy, positive pregnancy test prior to the enrollment or intention to become
393 pregnant.
394 5.
395 6. Subjects who will not tolerate liraglutide dose increase to 1.2 or 1.8 mg will remain in
396 the study at the highest tolerated dose

397 **Subject Replacement**

398 There will be no replacement of subjects in this trial.

399

400 **Rationale for Study Population**

401 We anticipate that approximately 400 patients will be screened in a 2-year period. We will
402 recruit patients with T2DM and clinically and angiographically stable CAD who will
403 undergo CABG surgery, as part of their standard medical care. Cardiac surgery will be
404 elective procedure in hemodynamically stable patients taking their standard cardiac
405 treatments and under the care of the cardiologist.

406

407 **Recruitment strategy:** Participants will be recruited among the outpatient population who
408 routinely refer to the Division of Cardiothoracic Surgery ([name] and collaborators),
409 Division of Cardiology ([name]) and Division of Endocrinology, Diabetes and
410 Metabolism outpatient clinics ([name]), at University of Miami.

411 **Visit Procedures**

412 **Study Timetable:** This study will consist of two clinical visits prior the cardiac surgery
413 and adipose tissue collection during the surgical intervention. Consecutive subjects with
414 T2DM and CAD who are candidate for elective cardiac surgery regardless of their
415 participation in the study will be selected, informed and consented. Patients suitable to
416 wait 12 weeks for cardiac surgery will be identified by the cardiology team and accordingly
417 scheduled, as part of the standard care. Anthropometrics, blood draw for laboratory
418 measures and echocardiographic measurements of EAT thickness will be performed at

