572 **Subject Compliance**

573 We estimate that the majority of the participants who will be considered eligible will
574 complete the study. Attrition can be estimated as lower than 10%. In the event that
575 participants are lost to follow-up, the research coordinator will contact with the study
576 participant by telephone. The research coordinator will be trained in effective telephone
577 technique to maximize recruitment success. All groups will receive lifestyle and diabetes
578 education, as part of the standard care, to insure similar glycemic control between arms.
579 Study patients will be advised to monitor their capillary glucose twice daily, fasting in the
580 morning and post-prandially. Glucose profile will be tracked bi-weekly by the research
581 coordinator by email or telephone.

582

583 **Statistical Considerations**

584 POWER ANALYSIS

585 The statistical power (two-sided, $\alpha=0.05$) of the study was calculated to detect statistically
586 and clinically meaningful differences in the primary endpoint between the two study arms.
587 Our preliminary data showed that EAT inflammatory genes, including IL-6 and TNF- α are
588 upregulated in subjects with T2DM and CAD and higher in EAT as compared to SAT⁴⁻¹⁷.
589 From our recently published study, we calculated the average coefficient of variance (CV)
590 for differential inflammatory genes to be 42%, but for only 5 T2DM patients.¹⁷ As there
591 are no data on the effects of liraglutide on EAT inflammation, the power analysis was based
592 on our previous data and on the assumption that the difference in EAT TNF- α and IL-6
593 expression between liraglutide treated and placebo treated patients would be clinically
594 meaningful at 33% (approx. 1.3X fold). Based on these data, we propose to sample 40
595 individuals. There will be 20 on liraglutide plus standard therapy versus 20 subjects on
596 liraglutide-matching placebo plus standard therapy contributing EAT and SAT samples
597 collected during cardiac surgery. Using the power set at 90% and $\alpha=0.05$, and given the
598 CV of 42%, this sample size will provide adequate power to detect the clinically significant
599 expected difference (33%) in EAT TNF- α and IL-6 between the two study arms.

600 Based on pre-existing data, this sample size will provide adequate power to detect
601 statistically significant differences in EAT TNF- α and IL-6 between the two study arms in

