602 those patients who will receive treatment only for 3 weeks. The difference in EAT TNF- α
603 and IL-6 between liraglutide treated and placebo treated patients is expected to be
604 approximately 1X fold after 3 weeks of treatment.

605

606 The larger sample proposed in this current project would likely reduce the variability. To
607 further assure consistency of results, mRNA and protein expression values will be log-

608 transformed prior to statistical analyses unless they will be normally distributed.
 609 Housekeeping genes will be also used for both RT-PCR and western blot analyses.
 610 In those patients who will not complete the 12-week treatment, the analysis of EAT genes
 611 from the samples will be time adjusted

612
 613 Statistical power was also calculated to detect statistically significant differences in the
 614 ultrasound measured EAT thickness, secondary endpoint, between the two study arms Our
 615 group very recently showed that additional therapy with liraglutide for 12 weeks caused a
 616 reduction in ultrasound measured EAT from 9.6 ± 2 to 6.2 ± 1.5 mm ($p < 0.001$) in 54 patients
 617 with T2DM ¹¹. Given the reference value and the expected difference in EAT, the
 618 statistical power of the study (two-sided, $\alpha = 0.05$) was calculated.

619

Outcome	Reference value \pm SD	Expected Difference	Detectable difference with 80% power $\alpha = 0.05$	Detectable difference with >99% power $\alpha = 0.05$
EAT (mm)	9.6 ± 2	-20-or -30%	-20% (absolute difference = 1.9)	-30% (absolute difference = 2.88)

620

621 Assuming a difference of approximately 2 mm (20%) in EAT to be clinically significant
 622 (based on our recent and previously published data ¹⁰⁻¹⁴), a convenience sample of 20
 623 individuals for each group will therefore provide at least the statistical power (80%) to
 624 detect an expected difference of at least -20% in the EAT before and after treatment with
 625 liraglutide. Baseline standard Deviation (SDs) of 2 is expected to lower to approximately
 626 1.5 for the expected change. The expected change of SD will further assure significant
 627 statistical power of the comparative test.

628

629 In those study patients who will not be able to complete the 12-week treatment, we
 630 anticipate to see a 15% of EAT reduction after 3 weeks in patients who will be allocated to
 631 liraglutide. This anticipated 15% of EAT reduction will remain clinically significant. For

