 632 example, a EAT thickness of 10 mm may likely decrease to 8.5 mm after 3 weeks of
 633 treatment with liraglutide, a clinically meaningful change for the patient cardio-metabolic
 634 profile.

635

636 This sample size also considers the difficulties with recruitment in the real world clinics.
 637 Based on our previous studies in humans, some participants may be lost to follow-up.

638

639 Student's t-test or non-parametric (Mann-Whitney) tests, depending on whether the genes
 640 mRNA expression and protein present or not a normal distribution, will be used to compare
 641 the effects of treatment (liraglutide versus placebo) on the variables measured. Student's
 642 t-test will be also used to compare ultrasound measured EAT thickness before and after
 643 treatments. Continuous variables will be considered as age-adjusted, sex-adjusted and
 644 weight-adjusted means with their SDs or median, if values are skewed.

645 Univariate regression models will be performed to assess the correlation between clinical
646 variables, including echocardiographic EAT thickness and blood tests, and EAT gene and
647 protein expression. Two-tailed $p < 0.05$ indicates statistical significance.

648

649 **Data Handling and Record Keeping**

650 Each of the dedicated clinic exam rooms provides direct access to the clinical research
651 study electronic data capture (EDC) eVelos system provided by the Clinical Research
652 Informatics and Data Management Unit of the Center for Health Informatics and
653 Bioinformatics at University of Miami (UM). The investigator and research coordinator
654 will collect and manage the data.

655 Data collection records with personal identifiers will be stored in locked file cabinets, at
656 [name]. Blood samples drawn
657 and stored in conjunction with this study will not be labeled with information that could
658 directly identify study subjects. Presentation of the study results at scientific meetings or
659 in publications will not identify subjects. Access to research and confidential records will
660 be limited to clinical investigators, research coordinators, and the IRB at UM.

661 **Adipose tissue samples storing**

662 Each adipose tissue sample will be snap frozen in liquid nitrogen and stored at -80°C until
663 analysis in a freezer, in [name] lab, University of Miami, Dept of Microbiology, 1600

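### The 90% power stated for the primary endpoint does not follow from its own inputs: 20 per arm, a 33% difference and CV 42% give about 68% on the plain reading, and 52% to 86% across six readings

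*Combined protocol and SAP*

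**What the plan says.** All inputs are in the Power Analysis part of Statistical Considerations, unless another place is named.

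- **Error rate and power:** two-sided alpha 0.05; "Using the power set at 90% and" the same alpha.
- **Effect:** a difference between liraglutide and placebo in EAT TNF-α and IL-6 taken as clinically "meaningful at 33% (approx. 1.3X fold). Based on these data, we propose to sample 40" patients, 20 in each arm.
- **Variability:** the authors calculated the average CV "for differential inflammatory genes to be 42%, but for only 5 T2DM patients".
- **Claim:** given the "CV of 42%, this sample size will provide adequate power to detect the clinically significant" 33% difference between arms.
- **Scale:** expression values will be log-"transformed prior to statistical analyses unless they will be normally distributed". The power statement does not say which scale it used, which arm the 33% refers to, or what formula was applied.
- **Test:** later in Statistical Considerations, a Student's t-test or Mann-Whitney test is named to compare "the effects of treatment (liraglutide versus placebo) on the variables measured".
- **Losses:** Subject Compliance says "Attrition can be estimated as lower than 10"%. Subject Replacement says "There will be no replacement of subjects in this trial".

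**The concern.** A 33% difference against a 42% CV is a standardised difference of roughly 0.8. Twenty per arm is well short of what 90% power usually needs for an effect of that size, so the claim called for recalculation.

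This is the only numeric power figure for the primary endpoint, and the plan bases its proposal of 40 patients on these data. If the true risk of missing the target difference is well above the implied 10%, a null result could be misread as good evidence against a 33% effect.

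**Working it through.** **Method.** Two-sample t-test, equal arms of n, two-sided 0.05. Power is P(|T| > t₀.₉₇₅,₂ₙ₋₂), where T is noncentral t with noncentrality d·√(n/2). For n = 20 the critical value is 2.024 and √(n/2) = 3.162.

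**Check of the method on the plan's other calculation.** The EAT thickness table uses SD 2 mm and differences of 1.9 and 2.88 mm. With 20 per arm, d = 0.95 gives 83% and d = 1.44 gives 99.3%. These agree with the table's 80% and >99%. The same formula should therefore be fair to the primary endpoint.

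**Plain reading.** d = 0.33/0.42 = 0.786; noncentrality 0.786 × 3.162 = 2.485; power 67.8%. The normal approximation gives 70.0%. The stated 90% is not reproduced.

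**Other readings at CV 42%.**

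- *SD proportional to the mean.* With liraglutide at 67% of placebo, the pooled SD is √[(0.42² + (0.42 × 0.67)²)/2] = 0.357 and d = 0.923. With placebo at 133% of liraglutide, the SD is 0.494 and d = 0.668.
- *Log scale.* SD = √ln(1 + 0.42²) = 0.403. A 1.3-fold difference gives d = 0.262/0.403 = 0.651; 1.33-fold gives 0.285/0.403 = 0.708; a ratio of 0.67 gives 0.400/0.403 = 0.994.

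| Reading | d | Power, 20/arm | Power, 18/arm | n per arm for 90% | CV giving 90% at 20/arm |
|---|---|---|---|---|---|
| Raw, common SD | 0.786 | 67.8% | 62.9% | 36 | 31% |
| Raw, SD ∝ mean, 33% lower | 0.923 | 81.2% | 76.7% | 26 | – |
| Raw, SD ∝ mean, 33% higher | 0.668 | 53.9% | 49.5% | 49 | – |
| Log, 1.3-fold | 0.651 | 51.8% | 47.5% | 51 | 25% |
| Log, 1.33-fold | 0.708 | 58.7% | 54.1% | 43 | 28% |
| Log, ratio 0.67 | 0.994 | 86.5% | 82.5% | 23 | 39% |

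Eighteen per arm is the bound implied by 10% attrition without replacement. Simulation with 100,000 trials confirmed the log-scale figures and the two readings with SD proportional to the mean. A Mann-Whitney test would do slightly worse: about 66% (plain) and 85% (log, ratio 0.67), using its 3/π efficiency.

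**What 20 per arm can detect.** d must be 1.052 for 90% power and 0.909 for 80%. On the raw scale these are 1.052 × 0.42 = 44% and 0.909 × 0.42 = 38%. On the log scale the ratios are exp(−1.052 × 0.403) = 0.65 and exp(−0.909 × 0.403) = 0.69.

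**Sensitivity to the CV, 20 per arm.**

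| CV | Raw, common SD | Log, 1.33-fold | Log, ratio 0.67 |
|---|---|---|---|
| 30% | 92% | 85% | 99% |
| 40% | 72% | 63% | 89% |
| 50% | 53% | 46% | 74% |
| 60% | 40% | 35% | 60% |

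**Variants that do give about 90%.** These are a one-sided test at log ratio 0.67 (92.5%), a one-sample or paired test with n = 20 on the plain reading (91.5%), and 40 per arm on the plain reading (93.5%). Each contradicts the stated two-sided comparison between arms with 20 per arm. Pairing is also not available for tissue, because fat is collected only at surgery.

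**The case against.** The strongest reply is that 68% is only one choice of scale. The plan log-transforms by default and hypothesises lower expression on liraglutide, so a 33% reduction on the log scale is a natural reading. It gives 86.5% by t-test and 88.1% by normal approximation, and needs 23 per arm against the planned 20. This stands in part: on that reading the shortfall is small. But a ratio of 0.67 is a 1/0.67 = 1.49-fold difference, whereas the plan equates its 33% with about 1.3-fold. At 1.3-fold, log-scale power is 52%.

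Other points on that side:

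- *The range is not a bound.* This is correct. It covers six readings; using 0.42 directly as the log SD with a 1.3-fold difference gives 48.6%.
- *N has other grounds.* The plan also calls 20 per group a sample of convenience in the thickness calculation, and cites recruitment difficulty. That may defend N = 40, but not the 90%.
- *Covariate adjustment could help.* The plan mentions means adjusted for age, sex and weight. Ignoring lost degrees of freedom, covariates would have to explain about 11% of the variance (log, ratio 0.67) or 44% (plain) to reach 90%. The stated calculation does not invoke adjustment.
- *The CV is too uncertain for any point figure.* With 5 patients, a rough normal-theory 95% interval around an SD of 0.42 is 0.25 to 1.21. This is a reason to show sensitivity, not to keep 90%.
- *A larger sample would reduce variability, as the plan suggests.* It makes the means more precise, which the formula already counts. It does not lower the CV between patients.

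**Conclusion.** The concern holds. No two-sided between-arm reading tried with the stated inputs gives 90%. Power is 68% on the plain reading and 52% to 86% across the six readings, so the risk of missing the target difference is 32% (range 14% to 48%) against the implied 10%. With 10% attrition the plain figure falls to 63%.

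The failure to reproduce 90% is firm. Its size depends on the scale and direction, which the plan leaves open. The figures assume CV 42%, an unadjusted t-test and one marker tested at 0.05. This must be fixed, because the main quantitative claim for the primary endpoint fails on its own inputs.

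**What to change.** Keep N = 40. Delete the 90% statement and replace it with the achieved power, naming the scale and the reference arm. Use one of these versions and do not mix them.

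> *Raw scale.* With 20 per arm, CV 42% and two-sided alpha 0.05, power for a difference of 33% of the placebo mean (common SD) is about 68%, down to 63% with 10% attrition. The detectable difference is about 44% at 90% power and 38% at 80% power.

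> *Log scale (SD about 0.40).* With 20 per arm and two-sided alpha 0.05, power is about 59% for a 1.33-fold difference [or: 86% for a liraglutide/placebo ratio of 0.67]. The detectable ratio is about 0.65 at 90% power and 0.69 at 80% power.

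The log version cannot be inserted until the sponsor says whether 33% means a 1.33-fold difference or a ratio of 0.67, and brings the 1.3-fold gloss into line.

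Add a line with power at CVs of 30%, 40%, 50% and 60% on the chosen scale (values in the second table above), because the 42% comes from 5 patients. State also that the figure is per marker and for an unadjusted t-test.

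The cost is protocol wording only: N, the test and the endpoint are unchanged. The stated power becomes less favourable.
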